9.2. Summary of findings from clinical studies

Both diagnostic tests had a high sensitivity (overall 97%) and specificity (overall 99%) in US FDA product registration trials (available from <https://www.biofiredx.com/support/documents/> under Instructions for Use and Manuals) and in independent research [23]. In a performance study that compared the BioFire RP2 Panel to the BioFire RP Panel or PCR and sequencing, the overall percent agreement between the BioFire RP2 Panel and the comparator testing was 99.2% [24].

Biofire respiratory panels:

Several studies have been conducted to examine the clinical impact of the BioFire RP Panel. Findings from such studies included an increase in diagnostic yield, decrease time to diagnosis, lower probabilities of hospital admission, reduced time in isolation, reduced number of supplementary tests such as chest radiographs, reduced hospital length of stay, decreased duration of antimicrobials use, and increase in appropriate antiviral use [25, 26].

As a rapid syndromic diagnostic testing it expedites turnaround time for results, leading to higher rates of early discharge and early discontinuation of antibiotics [27]. In a large retrospective study in paediatric patients with acute viral respiratory tract infections its use was associated with less exposure to antibiotics and chest X-rays and more timely administration of antivirals [28].

BioFire Pneumonia Panel:

Several studies have demonstrated the diagnostic yield and accuracy of the BioFire FilmArray Pneumonia Panel for identification of pathogens in lower respiratory tract specimens and show highly concordant results with optimal sensitivity and specificity for the detection of bacteria and viruses [29-34]. Single-country clinical trials (ClinicalTrials.gov) in community acquired pneumonia are currently active: CAP-NEXT (NCT03360851), PROARRAY (NCT03840603),

RADICAP (NCT04158492) and ventilator associated pneumonia: INHALE <https://fundingawards.nihr.ac.uk/award/RP-PG-0514-20018> are currently recruiting patients. Other single-center active projects, not recruiting: NCT02880384 and NCT03756753.

9.3. Summary of known and potential risks and benefits

Based on the BioFire FilmArray antibiotics may be withheld when deemed unnecessary, or a different antibiotic class may be selected when certain bacterial pathogens are detected. These management decisions are made by the patient's treating physician. The risks and benefits of these management decisions are subject to the current investigation.

A risk assessment and monitoring plan will be implemented but based on known intended use of the test (see below). Special effort will be invested on adequate training and monitoring of the sites (both laboratory and clinicians) for an optimal use of the test, and to support in the clinical and therapeutic decisions based on test results.

Safety and warning precautions of the product are summarised in the Instructions for Use as well as the Summary of Results and Limitations, with focus on the following:

- The pneumonia panel detects more pathogens than culture, however, the clinical significance may be unclear regarding their role as commensals, there might be concern for increasing antibiotic usage. Detection of bacterial nucleic acid may be indicative of colonizing or normal respiratory flora and may not indicate the causative agent.
- Asymptomatic carriage of viruses does occur, although less so in adults, or the virus could be a co-pathogen together with a bacterial pathogen, or a recent viral infection could have predisposed to a secondary bacterial pneumonia.
- Negative results in the setting of a respiratory illness may be due to infection with pathogens that are not detected by this test and pathogens below the limit of detection
- Negative results for antimicrobial resistance gene assays do not indicate susceptibility to corresponding classes of antimicrobials, as multiple mechanisms of antimicrobial resistance exist.
- There is a risk of false positive results due to non-specific amplification and/or cross-reactivity with organisms found in the respiratory tract and they are summarized in the Instructions for use. Erroneous results due to cross-reactivity with organisms that were not evaluated or new variant sequences that emerge is also possible.

Expected **benefits of the study** are, together with the main objective of reducing hospitalisation rates and antimicrobial use without adverse outcome, the opportunity for improved training, harmonised improvement of existing guidelines (local and European), opportunity to grow the different existing networks, opportunity to improve surveillance because of underreporting or not available diagnostic tests.

10. METHODS

[figure not shown]
10.1. Screening and enrolment

Patients entering the emergency room will be screened for study. When exclusion criteria 7-9 are unknown at the time of screening, patients will be enrolled nonetheless when they meet these inclusion criteria. After informed consent is obtained, remaining exclusion criteria will be checked.

The health status of patients might rapidly deteriorate between entering the emergency room and randomisation. Therefore, all eligibility criteria need to be re-evaluated and confirmed prior to the decision to randomise the patient.

Screen failures are defined as patients who were found eligible per screening and have given their consent to participate in the trial, but meet exclusion criteria 7 to 9 or did not meet all inclusion criteria anymore, during the evaluation of exclusion criteria 7 to 9. Of note, no diagnostic procedures such as chest radiograph will be performed for the purpose of checking eligibility criteria, only if indicated as standard of care. E.g. “if a chest radiograph is not deemed necessary by the treating physician, a pneumonia (exclusion criterion 7) cannot be excluded, but the patient can still be enrolled as there is no ‘radiologically confirmed acute lobar pneumonia’. When all criteria are met, the patient will be randomised (see next paragraph).

Figure 1. Study flowchart

*Radiologically confirmed acute lobar pneumonia, known or suspected *Pneumocystis jirovecii* pneumonia or active tuberculosis, alternative noninfectious diagnosis that explains clinical symptoms (pulmonary embolism, alveolar hemorrhage, acute heart failure, lung cancer)

ER: emergency room

10.2. Randomisation and blinding

Due to the nature of the intervention, blinding is not possible. After all eligibility criteria have been verified and informed consent has been obtained, randomisation will be performed using the built-in randomisation module of the eCRF system. Allocation will be concealed until the moment of randomisation. To this end, block randomisation will be used with variable blocks of size 2, 4 and 6. Randomisation will be stratified by centre. After the decision to randomise the patient is made, patients will not be excluded from the trial. If the allocated intervention is not applied for any reason, this will be recorded and follow-up for the participant will be completed.

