7. STUDY DESIGN AND DURATION

7.1. Study design and justification

This is a prospective, multi-centre, **individually randomised controlled open-label trial**. Approximately 1600 patients will be randomised in the trial in up to 10 investigational sites in the European region. Patients will be followed at day 14 and day 30 after randomisation. In a subset of patients, follow up will be extended to time points 3 and 6 months.

Enrolment will be competitive across sites.

Justification of the design. The aim is to deliver a study outcome that is **valid** (absence of bias), **precise** (sufficiently powered to achieve clinically relevant absence and presence of difference), and **generalizable** (recognizable population). The study needs to be **feasible** in terms of costs

(determined by number of study sites and number of tests to be performed), with an easy patient enrolment and an achievable burden on laboratories in both adult and paediatric sites. Therefore, although an **individually randomised trial** - in contrast to cluster randomisation - requires informed consent from all recruited patients fulfilling inclusion criteria prior to performing the test. This approach has several advantages: 1. Internal validity of the trial is guaranteed by the randomisation, whereas in cluster-randomised trials, patient selection criteria can be difficult to apply in a consistent manner, inducing a risk of selection bias; 2. Required sample size is lower compared to a cluster-randomised trial; 3. Recognizable population can be realized, although generalizability will always be lower compared to enrolling all-comers; 4. Feasibility: compared to a cluster-randomised trial, a lower sample size is needed, reducing costs for study execution; fewer hospitals, fewer patients, and a lesser burden on labs because tests are only performed in 50% of enrolled patients instead of 100% of all-comers. Moreover, although requirement of informed consent to be obtained at the ER could be considered as a drawback of this design, it in fact may help in enrolling the pursued patient population for this specific trial. We aim for patients in which the result of the rapid syndromic testing can guide clinical decision making. This implies that there is also time for obtaining informed consent.

In choosing the primary endpoints the following considerations were made:

- The composite endpoint is designed to capture the relevant outcomes and will be combined for analysis

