8.2. Inclusion criteria

1. **Adults** (≥18 years old) presenting to the **Emergency Room** with an **acute illness** (present for **14 days or less**) with **cough, and** with at least 1 other lower respiratory tract **symptom** or **clinical sign** at physical examination:
 - Sputum production,
 - Breathlessness,
 - Chest discomfort or chest pain,
 - Wheeze,
 - Crackles,
 - Self-reported dyspnoea or documented fever;
 - Documented hypoxemia (adjusting definition for chronic oxygen therapy users, method of measurement) **and no alternative explanation** (infection, such as sinusitis; other, such as asthma).
2. **Managing medical team considers** early in the diagnostic process:
 - a. to treat patient with antibiotics and/or to hospitalise patient

AND

 - b. that the rapid syndromic diagnostic test result can be awaited up to a maximum of 4 hours before the decision to discharge the patient or to initiate antibiotic therapy.

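### Section 10.2 prints small varying blocks (2, 4, 6) in an open-label, centre-stratified trial and credits them with concealment; the concealment comes from the eCRF module, and small known blocks weaken it

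*Combined protocol and SAP*

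**What the plan says.** Section 10.2 (Randomisation and blinding) describes the procedure in a few sentences. It states "Due to the nature of the intervention, blinding is not possible", and that "randomisation will be performed using the built-in randomisation module of the eCRF system" once eligibility is verified and consent obtained. It then links two ideas: "Allocation will be concealed until the moment of randomisation. To this end, block randomisation will be used". The sizes stand in the same sentence: "block randomisation will be used with variable blocks of size 2, 4 and 6". The only stratification factor is the site: "Randomisation will be stratified by centre". Section 7.1 calls the study an "individually randomised controlled open-label trial".

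On entry, section 8.2 requires that the managing team is considering "to treat patient with antibiotics and/or to hospitalise patient" and judges that the test result can be awaited. Section 10.1 has all eligibility criteria checked again just before the decision to randomise. Section 10.2 bars exclusion only after that decision.

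The protocol does not give the probability of each block size, does not say who at a site can see the running list of allocations, and does not say that the sizes are withheld from recruiting staff.

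**The concern.** Concealment and blocking are different things. A central electronic module conceals the next allocation by not releasing it until the patient is committed. Blocking keeps the arms balanced, and it does so by making later allocations in a block depend on earlier ones. When past allocations are visible, as in an open-label trial with one sequence per centre, that dependence gives away information. The smaller the blocks, and the better their sizes are known, the more it gives away.

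This matters more here than in a trial with purely objective entry criteria. Whether the team is considering antibiotics or admission, and whether the result can wait, are judgements made before randomisation. They also bear on the two superiority endpoints: days on antibiotics and days alive out of hospital. If an expected allocation influenced those judgements, the arms could differ in prognosis at baseline. Section 7.1 relies on randomisation to secure internal validity, so the step that protects randomisation should be described correctly and set up well.

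**Working it through.** The plan gives no figure for predictability, so there is none to reproduce.

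**Inputs.** Block sizes 2, 4 and 6, centre strata and no blinding (section 10.2); 1:1 allocation, inferred from half of patients being tested (section 7.1); about 1600 patients in up to 10 sites (section 7.1), so 1600/10 = 160 per centre on average if 10 take part. Equal probability of the three sizes is an assumption, varied below.

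**Step 1: average guess rate, exact.** Guess the arm that is behind, and toss a coin when the arms are level. For a block of size b = 2m the expected number of correct guesses is m + (4^m / C(2m, m) − 1)/2.

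- b = 2: 1 + (4/2 − 1)/2 = 1.50, or 75.0%
- b = 4: 2 + (16/6 − 1)/2 = 2.83, or 70.8%
- b = 6: 3 + (64/20 − 1)/2 = 4.10, or 68.3%

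With equally likely sizes: (1.50 + 2.83 + 4.10)/12 = 8.43/12 = 70.3%, against 50% by chance. The same formula gives 68.1% for 4/6/8. For 8/10/12 it gives (5.33 + 6.53 + 7.72)/30 = 65.3%.

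**Step 2: how confident the guesses are.** This was simulated with 400 sequences of 160 patients. The observer knows the sizes, their probabilities and every earlier allocation at the centre, but not where blocks begin, and updates by Bayes' rule.

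| Share of allocations | 2/4/6 | 4/6/8 | 8/10/12 |
|---|---|---|---|
| Guessed correctly overall | 70% | 68% | 65% |
| Called with ≥60% certainty | 59% | 64% | 64% |
| Called with ≥75% certainty | 59% | 34% | 21% |
| Called with ≥80% certainty | 52% | 24% | 12% |
| Called with ≥90% certainty | 6% | 5% | 3% |
| Certain | 4% | 2% | 1% |
| Pure coin toss | 41% | 36% | 31% |

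For 2/4/6, calls made with at least 75% certainty are right about 84% of the time. The two steps agree: 0.41 × 0.50 + 0.59 × 0.84 = 0.70.

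**Step 3: sensitivity.** With sequences of 20 or 40 patients the 2/4/6 results are essentially unchanged (70% correct, 59% called at ≥75%). With size weights 0.5/0.3/0.2 on 2/4/6 the share called at ≥75% is about 57%; with 0.2/0.3/0.5 it is 53%. Across the weights tried, 69 to 71% are guessed correctly, 3 to 5% are certain and 39 to 43% are a coin toss.

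**Step 4: what varying the size already achieves.** Fixed blocks of 4 would give 70.8% correct but 33% certain. The varying sizes remove most of the certainty and leave the average guess rate almost unchanged.

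**Step 5: the price of larger blocks.** The largest imbalance within a centre is half the largest block: 6/2 = 3 now, and 12/2 = 6 with 8/10/12.

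**The case against.** The strongest reply is that concealment in the usual sense is sound. The module releases the allocation only after eligibility and consent, nobody is excluded after the decision to randomise, the primary analysis is by intention to treat (section 13.2), and the primary models adjust for age groups and predefined risk factors (section 13.3). On this view the linking phrase in section 10.2 is only loose drafting. Much of this stands. However, none of these safeguards acts on the choice of whom to bring to randomisation, and adjustment for measured factors does not remove selection on unmeasured clinical judgement.

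A second reply is that the figures are a ceiling. They need someone who follows every allocation at the centre in order, in a working emergency department, and the documents do not show that the person judging eligibility can do so. This stands.

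A third is that the contrast between schemes depends on the threshold. At 90% certainty the three schemes give 6%, 5% and 3%, at 60% the larger blocks are slightly worse, and the overall guess rate falls by only 2 to 5 points. This also stands, and it limits what the change can be said to achieve.

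Two stronger readings are tempting. A reader might infer that recruiters can predict most upcoming allocations. The 59% refers to calls with at least 75% certainty, of which some are wrong: 0.59 × 0.84 is about half of all allocations. A further 41% cannot be predicted at all. A reader might also infer that the endpoints will be biased. That requires staff both to predict and to act on the prediction, and nothing in the documents shows either.

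**Conclusion.** The point holds as an avoidable weakness in design and drafting. Section 10.2 gives the wrong reason for concealment and prints small block sizes, including 2, in a protocol that sites hold. For a fully informed recruiter at a centre this allows about 70% correct guesses against 50%, and about 59% of allocations called with at least 75% certainty (53 to 59% under the other size weights tried). About 41% remain a coin toss and about 4% are certain.

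These are upper bounds. They rest on complete, ordered knowledge of the centre's allocations, known block sizes, 1:1 allocation and the assumed size probabilities. They describe an opportunity before randomisation that no stated safeguard closes. They do not show that selective enrolment occurs, and the direction and size of any resulting bias cannot be derived from the documents. A change is worth making because it is cheap; the validity of the trial is not shown to be compromised.

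**What to change.** In section 10.2:

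- Drop block size 2 and use larger varying blocks, for example 8, 10 and 12. The option 4, 6 and 8 gains less (68% correct and 34% called at ≥75%, against 65% and 21%).
- Move the sizes and their probabilities to a restricted randomisation document, and say in the protocol only that varying blocks stratified by centre are used.
- Attribute concealment to the eCRF module, and describe blocking as a means of balance.

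The larger blocks are the main change. Withholding the sizes does not by itself stop anyone from guessing the arm that is behind, and it does little at sites that already hold the present text. If recruitment has started, apply the new sizes to future blocks.

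The cost is one setting in the randomisation module and a short rewording. The maximum within-centre imbalance rises from 3 to 6, among about 160 patients per centre on average if 10 sites take part. No endpoint, sample size or analysis changes.

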10.3. Data collection

A secured electronic case record form (eCRF) will be specifically designed for this study for data capture.

- **Main study** (Follow up until 30 days) – Standard of care clinical and microbiological data will be collected but not study specific biological samples will be obtained for research purposes. The **clinical data set** will summarize the illness episode and outcome, microbiological testing and antimicrobial use including the total hospitalisation or, in case of discharge, the time window defined on the primary endpoints. Information including data for health economic analysis will be collected on day of enrolment, day 14 (visit window: day 14 – 16) and on day 30 (visit window: day 30 – 32), after randomisation. Participants/LAR will be asked to consent to being contacted by study staff for the follow-up visits to minimise loss to follow-up. In case of failure to successfully contact participant/LAR at the end of trial participation, the participant's general practitioner/family doctor will be contacted to complete information on the primary endpoints.
- **Extension study** – in a subset of patients (around 300 patients per arm), patients that were initially hospitalised will be followed post-discharge at month 3 (visit window: +7 days) and month 6 (visit window: +7 days) to study health economic and social impact.
- Qualitative Evaluation: Only clinician (semi-structured) qualitative interviews

10.4. Clinical data set

Inclusion. Check for inclusion and exclusion criteria and randomisation. Informed Consent Form.**Baseline registration and investigations.**

Signs and symptoms at ER and management plan

Participant background

Vaccination

Co-morbidities and chronic medication

Standard of care haematology and biochemistry

EQ-5D-5L questionnaire

Management: Clinical decision after randomisation and initial results

Investigations: respiratory, urine, faeces, blood, SARS-CoV-2, radiology (only when standard of care)

Day 14: symptoms, EQ-5D-5L questionnaire

Day 30: symptoms, EQ-5D-5L questionnaire

Month 3 (if applicable): symptoms, EQ-5D-5L questionnaire

Month 6 (if applicable): symptoms, EQ-5D-5L questionnaire

Outcomes and safety:

Antibiotic treatment

Antiviral and antifungal agents

Hospital course

Device deficiency

(Severe) Adverse Event

Deviation

End of study

Table 1. Visit Schedule

Procedures	Screening	Enrollment	Hospitalization Period ^e	Face to face, on line questionnaire or phone call		Phone call Extended FU	Phone call Extended FU
	Pre- study procedures	Day 1	> Day 1	Day 14	Day 30	3 months ^f	6 months ^f
	Day 1						
Informed consent	X						
Eligibility criteria	X						
Demographics ^a	X						
Baseline assessment ^b	X						
Vaccination status	X						
Comorbidities and chronic medications	X						
Hospital course ^c		X	X ^e				
Microbiological testing ^d		X	X				
Concomitant therapy review	X	X	X ^e	X	X	X ^f	X ^f
Symptoms review and hospitalizations	X	X	X ^e	X	X	X ^f	X ^f
Quality of life questionnaire EQ5D		X		X	X	X ^f	X ^f

10.5. Baseline and follow-up data for health-economic analysis

Follow up Assessments: Timepoints: Day 1, Day 14 and Day 30. · 3 months and 6 months for patients included in Extended Follow up

Individual patient data will be clustered in four main categories:

patient status prior to consultation (including quality of life assessment), diagnostics (including microbiological diagnostic tests and thoracic imaging), medicines (antibiotics and any other prescribed medication at the ER/admission including several parameters, antibiotic prescription in the previous 14 days) and patient follow-up (quality of life, adherence to treatment, duration of complaints).

Quality of life- (see eCRF completion guidelines on guidance) The EQ-5D (<https://euroqol.org>) contains 5-dimensions ("5D") related to everyday living: mobility, self-care, usual activities, pain/discomfort, and anxiety/depression. Patients rate the problems they have with each of these dimensions on a 5-level scale ("5-L") from 1 (no problems) to 5 (extreme problems). The second part of the EQ-5D-5L asks patients to grade their current global health status from 0 (worst health you can imagine) to 100 (best health you can image). The questionnaire form takes ± 5-10 min to administer. It needs to be completed by patient or person who has known the patient for > 5 years. (Order of preference: caregiver > spouse > children 18+ > sibling > other acquaintance). For patient questionnaires, patients will receive a link per email to complete the questionnaires online, which will directly be incorporated into the eCRF and be regarded as source data once digitally completed by the patients. If this is not possible or if patients are seen face to face, questionnaires will be completed per paper (source data) and entered in the eCRF by study staff at the site. In this case paper versions will be stored as source data. The third option to have the questionnaires completed is the use of the Interviewer version in which the study staff will interview the patient and complete the data on the paper form (source data) after which data will be entered in the eCRF.

